### 3.2.2. Open-Label Treatment Phase

- Achievement of corticosteroid tapering per protocol at the end of the open-label active treatment period in applicable subjects receiving corticosteroids on study Day 1 of the open-label phase.

A successfully tapered subject is one that has completed Part 2 of the OL by reaching their target corticosteroid dose and maintaining an adapted JIA ACR30 response for four weeks on this dose.

- Achievement of a corticosteroid dose of  $\leq 0.2$  mg/kg/day or 10 mg/day (whichever is lower) at the end of the open-label treatment period in subjects receiving corticosteroids on Day 1 of the open-label phase.
- Occurrence of CRP  $\leq 10$  mg/L at every visit of the open-label phase.
- Occurrence of fever (Temp  $>38$  Degrees Celsius) attributed to sJIA at Day 3, Day 7 and Day 14 of the open-label phase.
- Time from first tofacitinib dose to first adapted JIA ACR30 response in Part 1 of the open-label phase.
- Adapted JIA ACR 30/50/70/90/100 response at every visit from Day 7 onward in the open-label phase.
- “Absence of fever”, defined as absence of fever due to sJIA in the week preceding the assessment at every visit from Day 7 onward in the open-label phase.
- Change from OL baseline in Juvenile Arthritis Disease Activity Score (JADAS-27, calculated based the ESR and CRP inflammation biomarkers separately) at every visit from Day 7 onward in the open-label phase.
- Change from OL baseline in each JIA ACR core variable at every visit from Day 7 onward in the open-label phase.
- Occurrence of inactive disease status and minimal disease activity (JADAS-27, calculated based the ESR and CRP inflammation biomarkers separately) at every visit from Day 7 onward in the open-label phase.
- Occurrence of JIA ACR inactive disease status at every visit from Day 7 onward in the open-label phase.
- Change from OL baseline in Child Health Questionnaire (CHQ) responses at the end of Part 1 and Part 2 of the open-label phase.
- Change from OL baseline in Child Health Assessment Questionnaire (CHAQ) - Discomfort Index at every visit from Day 7 onward in the open-label phase.

For details of the derivation of the secondary endpoints, see [Appendix 3.1](#) to Appendix 3.9.

### **3.3. Other Endpoints**

#### **3.3.1. PK Endpoints**

- Tofacitinib concentrations during the open-label phase.

#### **3.3.2. Exploratory Endpoints**

- Change from OL baseline in various genomic and serum biomarkers following treatment with tofacitinib.

### **3.4. Baseline Variables**

This study will have a separate type of baseline for each of its two phases. The open-label baseline will be defined as the last value collected prior to day 1 of tofacitinib administration in this phase. For the analyses in the double-blind phase, baseline will refer to the values collected at the randomization visit – before the administration of the assigned treatment in this phase for all endpoints, unless noted otherwise. For Adapted JIA ACR responses the open-label baseline will be utilized as the reference point.

Selected analyses in the double-blind phase, such as changes in laboratory parameters and vital signs, will also refer to the open-label baseline as a separate analysis, in addition to using the double-blind baseline.

In the double-blind phase change from baseline in each sJIA ACR core variable will be calculated with respect to both the open-label and double-blind baseline.

Age groups for stratification will be based on the age at enrollment in the open-label phase of the study. The age groups are: 2 to <6 years, 6 to <12 years, and 12 to <18 years.

### **3.5. Safety Endpoints**

The safety endpoints of this study are:

- All adverse events (AEs), including Serious Adverse Events (SAEs).
- Adjudicated macrophage activation syndrome (MAS) events.
- Serious infections, including tuberculosis, varicella and herpes zoster and adjudicated opportunistic infections.
- Clinically significant abnormal laboratory parameters, including abnormal hematology parameters, lipid parameter changes, liver enzymes, serum creatinine elevation.
- Adjudicated malignancies, including lymphoma and non-melanoma skin cancer.
- Adjudicated gastrointestinal perforations.

- Adjudicated cardiovascular diseases.
- Assessments of growth and puberty development.

## 4. ANALYSIS SETS

### 4.1. Double-Blind Analysis Sets

#### 4.1.1. Double-Blind Full Analysis Set

The Double-Blind Full Analysis Set (DBFAS) will consist of all randomized subjects who received at least one dose of investigational product in the double-blind phase. Subjects will be reported under the treatment they were randomized to. In this study, the primary efficacy analysis will be performed on the DBFAS. Secondary endpoints for the double-blind randomized withdrawal phase will also be analyzed using the DBFAS.

#### 4.1.2. Double-Blind Safety Analysis Set

The double-blind safety analysis set (DBSAS) will consist of all randomized subjects who have received at least one dose of investigational product in the double-blind phase. Subjects will be reported under the treatment that they received. This analysis set will be very similar, if not the same, with the DBFAS; however, the subjects will be analyzed according to the treatment received rather than randomized.

### 4.2. Open-Label Analysis Sets

#### 4.2.1. Open-Label Part 1 Analysis Set

Open-label part 1 (OLPT1) analysis set will consist of all subjects who were enrolled into the open-label part 1 phase of the study and received at least one dose of investigational product in part 1.

#### 4.2.2. Open-Label Part 2 Analysis Set

Open-label part 2 (OLPT2) analysis set will consist of all subjects who were enrolled into the open-label part 2 phase of the study and received at least one dose of investigational product in part 2.

## 5. GENERAL METHODOLOGY AND CONVENTIONS

### 5.1. Hypotheses and Decision Rules

The primary null hypothesis in this study is that there is no difference between the distributions of time to disease flare in the double-blind randomized withdrawal phase between tofacitinib and placebo. The alternative hypothesis is that, among the subjects that meet the randomization criteria, time to disease flare is increased in the subjects remaining on tofacitinib in the double-blind withdrawal phase versus placebo subjects.

The difference between the distributions of time to disease flare will be tested using an unstratified log-rank test ([Schoenfeld, 1987](#); [Shih, 1999](#); [Yang, 2012](#)).

There will be potentially 2 planned analyses. The First Analysis will be performed after 28 subjects have reported flare in the double-blind phase. Number of flares required for the 2 planned analyses will be counted according to the definition of having a flare in the primary estimand ([Section 2.3.1](#)). The purpose of the First Analysis is to allow early stopping of the study for efficacy or futility, and to assess safety of tofacitinib. The investigators, subjects, and sponsor study team will remain blinded to treatment assignment in the double-blind phase through the entire duration of the trial until final database release.

If the study does not end for efficacy or futility at the First Analysis, a total of 37 subjects with flares will be required for the Final Analysis to yield an overall power of 80% using a log-rank test to detect the treatment difference, assuming a 1-sided type-I error rate of 2.5% and a 64% improvement in median time to flare (i.e., a hazard ratio of 0.36 and a median time to flare of 236 days for placebo; assumptions based on a similar sJIA randomized withdrawal trial). The number of flares needed at the Final Analysis will be based upon the actual number of flares at the First Analysis (additional details are provided below and in [Appendix 2](#)).

To protect the integrity of the study and to preserve the type I error rate at 0.025 (1-sided test) and overall study power at 80% (type II error rate  $\beta=0.2$ ), a fraction of  $\alpha$  for efficacy and a fraction of  $\beta$  for futility will be spent at the First Analysis and accounted for in the overall type I error rate and type II error rate, respectively. A formal efficacy boundary for rejecting the null hypothesis is constructed by using the spending function methodology of the gamma family design with  $\gamma= 4$ . Similarly, a formal futility boundary for not rejecting the null hypothesis is constructed by using the spending function methodology of the gamma family design with  $\gamma= -4$ .

- If the value of the test-statistic at the First Analysis crosses the efficacy boundary ( $z \leq -1.973$ , 1-sided  $p \leq 0.0242$ ), the trial may be stopped for efficacy.
- If the value of the test-statistic at the First Analysis crosses the futility boundary ( $z \geq -1.240$ , 1-sided  $p \geq 0.1074$ ), the trial may be stopped for futility.
- Otherwise, the trial will continue as planned. The Final Analysis will be performed after flares have been reported in 37 subjects.

**Table 2. Efficacy and Futility Stopping Boundaries with 28 Flares at First Analysis Expressed as Hazard Ratio, Z Scores and P-values**

Efficacy Stopping Boundary				
	Number of Flares	Hazard Ratio	Z-score	P-value (1-sided)
First Analysis	28	0.474	-1.973	0.0242
Final Analysis	37	0.427	-2.586	0.0049
Futility Stopping Boundary				
	Number of Flares	Hazard Ratio	Z-score	P-value (1-sided)
First Analysis	28	0.626	-1.240	0.1074

**Table 2. Efficacy and Futility Stopping Boundaries with 28 Flares at First Analysis Expressed as Hazard Ratio, Z Scales and P-values**

Final Analysis	37	0.427	-2.586	0.0049
----------------	----	-------	--------	--------

Assuming a hazard ratio of 0.36 (tofacitinib vs placebo) and a median time to flare of 236 days for placebo Randomization ratio = 1:1, type I error rate (1-sided) = 2.5%, power = 80.4%

Efficacy boundary: gamma family spending function with  $\gamma = 4$

Futility boundary (non-binding): gamma family spending function with  $\gamma = -4$

The efficacy and futility boundaries will depend on the number of flares. For logistical and administrative reasons, the actual number of flares at the First Analysis and the Final Analysis might differ slightly from those that have been pre-specified here. In that case appropriate adjustments will be made to the efficacy and futility boundaries. The actual boundaries used for the First or the Final Analysis will be re-calculated from the specified spending function based on the actual number of flares achieved at the time of First or Final analysis. These boundaries will be calculated prior to the evaluation of comparative data. More specifically, for the First Analysis, the study team will complete evaluation of subject data to determine the total number of flares in the primary analysis. The stopping boundaries and the number of flares needed at the Final Analysis will be calculated from the specified spending functions to preserve the type I error rate at 0.025 (1-sided test) and overall study power at 80% (type II error rate  $\beta=0.2$ ). Examples of efficacy and futility boundaries in various scenarios are provided in [Appendix 2](#).

The First Analysis will be completed by the independent Statistical Data Analysis Center (SDAC), and the results will be reviewed by the Data Safety Monitoring Board (DSMB). The efficacy and futility boundaries will be calculated as described above by the study statistician, and provided to DSMB prior to the First Analysis. Before the First Analysis is performed, the details of the objectives, decision criteria, dissemination plan and method of maintaining the study blind as per Pfizer's standard operating procedures will be documented and approved in a DSMB charter.

If the study continues and the total number of flares observed at the Final Analysis exceeds the number calculated at the First Analysis (e.g., 37 planned and 38 observed), the boundaries will be adjusted based on the actual information fraction (e.g,  $38/37=1.03$ ) to preserve the type I error rate. The adjusted boundaries will be determined prior to the evaluation of comparative data.

## 5.2. General Methods

In addition to the statistical methods described below, all efficacy endpoints listed in [Section 3](#) will be summarized descriptively. In general, number and percent will be presented for binary variables; number, mean, median, standard deviation, quartiles, minimum, and maximum will be presented for continuous variables. The Kaplan-Meier method will be used to obtain the estimates of median (and other percentiles) event free time for time-to-event endpoints and estimates of event free rates at specific time points.

The analyses in the double-blind phase will be performed by treatment group (tofacitinib and placebo), per [Section 5.2.5](#). For this time-to-event trial, subjects will have variable follow-up

times. Efficacy analyses by-visit in the double-blind randomized withdrawal phase will be performed at Week 4 and every 4 weeks through the last visit of the whole study. However, only the data through 52 weeks in the double-blind phase will be analyzed statistically ([Section 2.3.2](#)).

The analyses in the open-label phase will be performed separately for Part 1 and Part 2. The summaries will be presented for all tofacitinib.

All efficacy endpoints will be derived programmatically by Pfizer with the exception of double-blind flare, which will be based on real-time calculations by the CCC.

### 5.2.1. Analyses for Time-to-Event Data

Time-to-event endpoint, i.e., time-to-flare in the double-blind randomized withdrawal phase, will be summarized using the Kaplan-Meier method and estimated survival curves will be displayed graphically. The median and quartiles for the time to event and survival (event-free) probabilities at particular time points along with 95% confidence intervals (CIs) will be estimated. The 95% CIs for both the estimated probability of event and the probability differences between the treatment groups at the target day of each windowed visit ([Appendix 3.13](#)) will be generated using Greenwood's formula.

Details on the censoring of time-to-flare for the primary analysis can be found in [Section 6.1.1](#) and for supportive analyses can be found in [Section 6.1.2](#).

The unstratified log-rank test will be used to compare the time to event between the treatment groups.

Hazard ratios (tofacitinib/placebo) and 95% CIs will be obtained from a Cox Proportional hazards model with treatment group as covariate. Repeated confidence interval will also be provided to account for alpha spending, when appropriate. This will be done as a supportive analysis for the log-rank test comparison between the treatment groups.

### 5.2.2. Analyses for Binary Data

Open-label binary endpoints will be analyzed using the normal approximation to binomial proportion.

The normal approximation 95% CI is calculated as:

$$\hat{p} \pm z_{0.975} \sqrt{\frac{\hat{p}(1 - \hat{p})}{N}}$$

where  $\hat{p}$  is the estimated response rate,  $z_{0.975}$  is the 97.5th percentile of the standard normal distribution and N is the number of subjects evaluable for the endpoint at the time point. If the lower bound is calculated to be negative, it will be set to 0%; if the upper bound is calculated to be larger than 100%, it will be set to 100%. In case when response rate is 0 or 100%, standard error will be reported as "NA" and the 95% CI bounds will be the same as the response rate.

For the double-blind binary endpoint at a single time point (eg, adapted JIA ACR 30/50/70/90/100 response at each DB phase visit), the normal approximation for the difference in binomial proportions can be used to test the superiority of tofacitinib 5 mg BID to placebo at DB phase timepoints. The normal approximation to the test statistic for the difference in binomial random variables is calculated as

$$Z = \frac{\hat{p}_t - \hat{p}_c}{\sqrt{\frac{\hat{p}_t(1 - \hat{p}_t)}{N_t} + \frac{\hat{p}_c(1 - \hat{p}_c)}{N_c}}}$$

where  $\hat{p}$  refers to the relative frequency,  $N$  to the number of observations, the subscript  $c$  refers to the comparator group (e.g., placebo group) and the subscript  $t$  refers to the test group (e.g., tofacitinib 5 mg BID group) so that test statistics and p-values can be calculated for the contrast comparing the two treatment groups.

Two-sided 95% confidence intervals will be formed by

$$\hat{p}_t - \hat{p}_c \pm z_{0.975} \sqrt{\frac{\hat{p}_t(1 - \hat{p}_t)}{N_t} + \frac{\hat{p}_c(1 - \hat{p}_c)}{N_c}}$$

Two-sided p-value for the test of the 0 difference between tofacitinib 5 mg BID and placebo groups will be calculated as:

$$p = 2(1 - \Phi(|Z|)),$$

where  $\Phi(.)$  is the Gaussian cumulative density function.

If there is no (ie, 0) response or 100% response in any one or both of the two treatment groups for the comparison, eg, tofacitinib 5 mg BID vs. placebo, when calculating the proportions above, 0.5 will be added to the number of responses (ie, numerator) and 1 will be added to the denominator in each treatment corresponding to the pair of comparison for calculating the treatment difference, standard error (ie,  $\sqrt{var(d)}$ ), 95% CI and 2-sided p-value (Agresti, 2002). (Note that this adjusted method also applies to the case where the response rate is 0% in one treatment group and 100% in the other for comparison.)

When response rate of 0% is observed in both treatments or 100% in both treatments in comparison, no formal comparison will be performed. Estimated response rate of 0% or 100% will be reported as observed. Standard error will be reported as 0.

The final results will be expressed in percentages, i.e., (proportions x 100)%.

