10.3. Guidance to Open Enrollment following Cohort Review

In Part 1 of the open-label phase, dosing decisions will be made based on the evaluation of cohorts of 7 subjects treated with tofacitinib. Enrollment will be conducted in a staggered fashion. The Sponsor, under the guidance of a Steering Committee, will assess safety, efficacy, and pharmacokinetics of the 5 mg BID dose and advise on further enrollment and dosing with 5 mg BID in the study.

For efficacy, the upper limit of a 95% confidence interval (shown below) for an Adapted JIA ACR 30 response will serve as guidance to evaluate the initial cohorts of 7 subjects dosed with tofacitinib 5 mg BID.

Table 6. 95% Confidence Intervals for Adapted JIA ACR 30 Response in Open Label Cohorts

N (Total)	n (Responder)	p (Response Rate)	95% CI for p	
			Lower Limit	Upper Limit
7	0	0	0	0.410
7	1	0.143	0.004	0.579
7	2	0.285	0.037	0.710
7	3	0.429	0.099	0.816
7	4	0.571	0.184	0.901

A 95% confidence interval can be interpreted as: There is a 95% probability that the calculated confidence interval from sampling encompasses the true response rate for the population. Thus, if 1 out of 7 responders were observed in a cohort, a response rate of approximately 58% or higher could be ruled out with 95% confidence. Using the confidence interval, a given cohort will be deemed to have sufficient efficacy for further study if at least 2 responders out of 7 subjects are observed. The following will serve as guidance for making decisions about the cohorts:

- If ≤ 1 out of 7 responders is observed in 2 consecutive cohorts, the dose level will be discontinued.
- If ≥ 2 out of 7 responders are observed in each of 2 consecutive cohorts at the 5 mg BID dose level, efficacy at this dose level will be considered sufficient to allow further evaluated in additional subjects.
- In the event that intermediate response rates are observed (for example, 1 out of 7 in the first cohort and 2 out of 7 in the second), the decision on whether or not to evaluate the dose level in additional subjects would be based on review of the totality of the data by the Sponsor and Steering Committee and further cohort(s) may be needed to evaluate this dose.

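### SAP 5.2.2 gives open-label response rates of 0% or 100% a zero-width 95% interval whatever the sample size, although Protocol Table 6 uses exact limits for the same kind of data

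*SAP*

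**What the plan says.** **SAP 5.2.2, open-label endpoints.** The method is stated generally: "Open-label binary endpoints will be analyzed using the normal approximation to binomial proportion". The interval is the observed rate plus or minus 1.96 standard errors, cut off at 0% and 100%, where "N is the number of subjects evaluable for the endpoint at the time point". For the boundary there is a special rule. The standard error is given as NA, and "the 95% CI bounds will be the same as the response rate".

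**SAP 5.2.2, double-blind comparisons.** If either or both arms are at 0% or 100%, "0.5 will be added to the number of responses (ie, numerator) and 1 will be added to the denominator" in each arm. The next paragraph covers both arms at 0% or both at 100%. No formal comparison is then made, and "Standard error will be reported as 0".

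**Protocol 10.3.** The initial cohorts of 7 were to be judged by "the upper limit of a 95% confidence interval (shown below) for an Adapted JIA ACR 30 response". Table 6 gives 0 to 0.410 for 0 of 7 responders.

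**Whether open-label intervals are shown.** SAP 5.2 says descriptive summaries come in addition to the methods of its subsections, so the 5.2.2 interval applies. SAP 6.2.2 names only number and percentage for open-label binary endpoints. SAP Table 4 lists these endpoints as summaries with no analysis model.

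**The concern.** A 95% interval should show which true rates remain compatible with the data, and it should narrow as subjects are added. Under this rule 0 of 7 and 0 of 100 carry the same interval, and both appear to exclude every true rate above zero. The standard error of NA acknowledges that the formula gives no usable value at the boundary, yet the limits are set as if the error were zero.

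The sponsor handles the same problem properly elsewhere. Protocol Table 6 gives a non-zero upper limit at 0 of 7. For adverse-event incidence rates, SAP 6.6.1 uses exact Poisson limits with a non-zero upper limit when no events occur.

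At stake is how stringent open-label endpoints (for example Adapted JIA ACR 90/100 or inactive disease at early visits) and near-universal ones (absence of fever in Part 2) would read if a visit happens to show 0% or 100%.

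**Working it through.** **Inputs.** The interval formula and boundary rule are from SAP 5.2.2, and Table 6 is from Protocol 10.3. The SAP gives no number of subjects (N) per visit, so N is an illustrative assumption: 7 (cohort size), 12 (age-group enrolment target, Protocol 10.1), 50 (arbitrary) and 100 (approximate enrolment, Protocol 10.1).

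**Step 1: reproduce Table 6.** The exact (Clopper-Pearson) limits for x responders of N are:
- lower = 2.5% quantile of Beta(x, N − x + 1), or 0 if x = 0
- upper = 97.5% quantile of Beta(x + 1, N − x), or 1 if x = N

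For x = 0 the upper limit reduces to 1 − 0.025^(1/N). With N = 7 this is 1 − 0.5904 = 0.4096, the 0.410 of Table 6. All five rows agree to three decimals. The normal-approximation and Wilson intervals do not reproduce the table.

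| Responders of 7 | Table 6 | Exact | SAP 5.2.2 | Wilson |
|---|---|---|---|---|
| 0 | 0 to 0.410 | 0 to 0.410 | 0 to 0 | 0 to 0.354 |
| 1 | 0.004 to 0.579 | 0.004 to 0.579 | 0 to 0.402 | 0.026 to 0.513 |
| 2 | 0.037 to 0.710 | 0.037 to 0.710 | 0 to 0.620 | 0.082 to 0.641 |
| 3 | 0.099 to 0.816 | 0.099 to 0.816 | 0.062 to 0.795 | 0.158 to 0.750 |
| 4 | 0.184 to 0.901 | 0.184 to 0.901 | 0.205 to 0.938 | 0.250 to 0.842 |

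**Step 2: the SAP interval at the boundary.** The half-width is 1.96 × √(p(1 − p)/N). At p = 0 or p = 1 it is 1.96 × √(0/N) = 0 for every N. Moving from 1 of 7 to 0 of 7 therefore shrinks the interval from about 40 points wide to none.

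**Step 3: what a valid interval would show.** For 0 responders the exact upper limit is 1 − 0.025^(1/N), and the Wilson upper limit is z²/(N + z²) with z² = 3.8415.

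| N | SAP 5.2.2 | Exact upper limit | Wilson upper limit |
|---|---|---|---|
| 7 | 0% | 41.0% | 35.4% |
| 12 | 0% | 26.5% | 24.2% |
| 50 | 0% | 7.1% | 7.1% |
| 100 | 0% | 3.6% | 3.7% |

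At 100% response the limits mirror these. For 12 of 12 the exact lower limit is 100 − 26.5 = 73.5%.

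**Step 4: how often the rule would mislead at small N.** If the true rate were 10% (an assumption), the chance of seeing no responders, and so a zero-width interval that misses the truth, is 0.9^N: 47.8% at N = 7 and 28.2% at N = 12.

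**The case against.** The strongest reply is that little depends on this. Open-label endpoints are secondary, with no treatment comparison. SAP 6.2.2 and Table 4 list only number and percentage, so the interval may never be printed. That limits the impact, but 5.2.2 still prescribes the interval and 5.2 says descriptive summaries are additional. The two parts need reconciling.

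Several stronger readings are tempting, and the documents do not support them:

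- **That 0% and 100% are the least informative results.** At fixed N the opposite holds. In Table 6 the width is 0.410 for 0 of 7, against 0.816 − 0.099 = 0.717 for 3 of 7. The defect is the failed approximation.
- **That the SAP claims a standard error of zero for open-label rates.** It reports NA; only the limits collapse.
- **That the rule affected the cohort decisions.** Those relied on the Protocol 10.3 guidance, and Protocol 3.4.1 records that both cohorts are complete.
- **That age groups of about 12 will be shown this way.** SAP 6.4 plans no open-label subgroup analyses. Protocol 10.2.2 leaves some room, because it plans forest plots of intervals by age group in a paragraph that opens with the open-label phase.
- **That rates of 0% or 100% are to be expected.** They are plausible for some endpoints, but neither document gives expected rates by visit, and Protocol 3.2.2.2 allows for loss of response during tapering.
- **That the double-blind paragraphs flatly contradict each other.** The second can be read as a specific exception to the 0.5/1 adjustment, with no comparison made. What remains is a printed standard error of 0, where the same section uses NA for the single-rate boundary case.

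**Conclusion.** The point holds as a reporting defect. The open-label rule in SAP 5.2.2 yields an interval without 95% meaning whenever a rate is 0% or 100%, and it departs from the exact method the sponsor used in Protocol Table 6. The understatement is 26.5 percentage points at N = 12, 7.1 at N = 50 and 3.6 at N = 100. These sizes rest on assumed values of N. At visits with close to full enrolment the error is small; it matters most where few subjects are evaluable.

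It does not touch the primary log-rank analysis, type I error or sample size. It should be corrected because the rule is wrong as written and the remedy is cheap, not because a trial conclusion depends on it.

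**What to change.** 1. In SAP 5.2.2, replace the open-label rule for 0% and 100% with the exact (Clopper-Pearson) interval already used in Protocol Table 6, or with Wilson. Preferably use the same method for all open-label proportions, so that the method does not switch at the boundary.
2. In SAP 6.2.2, and to match in Table 4, state whether open-label intervals are presented.
3. In the double-blind paragraph on both arms at 0% or both at 100%, change the reported standard error from 0 to NA, and state that this case is an exception to the 0.5/1 adjustment.

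**Cost.** A few lines of wording and one program option. Intervals at 0% or 100% become wider, as they should. If the method is changed throughout, other intervals shift too: for 3 of 7, from 6.2–79.5% to 9.9–81.6% with exact limits.
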